3.9 Clinical Laboratory Assessments

Safety laboratory variables (i.e. hematology, biochemistry, and urinalysis results) will be presented in SI units at each time point using descriptive statistics (mean, standard deviation, median, minimum, and maximum). Change from baseline values for each variable will also be presented by treatment group. The number and percentage of patients with shift changes from baseline (normal/missing, high, and low according to the reference range) to the highest/lowest laboratory evaluation during the TEAE period will be tabulated by treatment group.

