
Study Population (cont'd)
	
 • Clinically abnormal renal function: serum creatinine > 132 μM (>1.5 mg/dL); • Clinically abnormal liver function: Total bilirubin >1.5 x ULN (in the absence of demonstrated Gilbert’s syndrome), ALT and/or AST > 2.5 x ULN; • Patients with plasma retinol levels below 0.7 μM; • Known history of a severe allergy or sensitivity to retinoids (e.g. vitamin A, isotretinoin, etretinate), or with known allergies to excipients in the oral capsule formulation to be used in the study; • History of organ transplantation; • History of alcoholism or drug abuse within 2 years before screening; • Presence of a cancerous tumor, active or in remission, treated or not, except squamous or basal cell carcinomas of the skin that have been treated and deemed resolved; • Presence of nyctalopia (also called night-blindness, a condition making it difficult or impossible to see well at night or in poor light) or hemeralopia (the inability to see in bright light) at enrolment, or any other serious retinal, ophthalmological condition (e.g.: retinitis pigmentosa, choroidoretinitis, xerophthalmia, uncontrolled glaucoma); • Presence of serious dermatological conditions at entry, including inflammatory or xerotic skin pathologies such as psoriasis or ichthyosis; • Intake of chronic systemic steroids in the month prior to screening and during the study. Inhaled corticosteroids for treating asthma/rhinitis are allowed as well as systemic corticosteroids (≤ 5 mg/day of prednisone or equivalent, or a higher loading dose tapered down in subsequent days) administered temporarily to control asthma exacerbations or pulmonary infections associated with bronchospasm (topical corticosteroids for dermatologic conditions may be allowed, subject to Investigator and Sponsor’s representative authorization); • History of acute infections (viral/bacterial/fungal) within 5 weeks prior to randomization, of which 2 weeks minimum are prior to screening, whether or not treated and resolved. Exceptions are topical skin infections under treatment/treated with a local non-prescription antibiotic; • Presence of infection with Burkholderia cepacia (including all species within the Burkholderia cepacia complex group, and Burkholderia gladioli) in the 12 months prior to screening (resolution of previous episode confirmed by quarterly negative cultures for the 12 months prior to screening); • Patients with a confirmed diagnosis (as per the CFF diagnostic criteria) of Allergic Bronchopulmonary Aspergillosis “ABPA” and actively being treated with corticosteroids and/or antifungal agents; • Participation in another drug clinical trial within 30 days, meaning from the last study drug administration of the prior study (or a minimum of 5 elimination half-lives) prior to screening; • Any other clinically significant condition that is considered by the principal investigator as being susceptible to put the patient at greater safety risk, influence response to study product, or interfere with study assessments.

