12.5.2 Clinical Laboratory Assessments

Safety laboratory variables (e.g., hematology, biochemistry, and urinalysis results) will be presented in SI units at each time point using descriptive statistics (mean, standard deviation, median, minimum, and maximum). Change from baseline values for each variable will also be presented by treatment group. The number and percentage of patients with shift changes from baseline (normal/missing, high, and low according to the reference range) to the highest/lowest laboratory evaluation during the TEAE period will be tabulated by treatment group.

Summary tables of laboratory results will be prepared to examine the worst toxicity grade on study. Cross-tabulations of patients by maximum post-baseline toxicity will be presented, as appropriate. Patients who develop Grade 3-4 laboratory toxicities will also be listed separately.

A Fisher's Exact test will be used in an exploratory sense to evaluate differences between treatment groups in the incidence of laboratory toxicities graded according to CTCAE grading outlined in section 11.1.1.1.

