5 METHODOLOGICAL CHANGES FROM PROTOCOL

SAP Version (date)	Relevant Section in Protocol (Amendment 3 – dated: 31JUL2019)	Section (s) and Change (s) in SAP	Rationale for Change
Final v5.0 (dated: 08OCT2019)	Protocol Section 12.2 (Analysis Population); PEx Analysis Subset Population	SAP Section 3.3. (Analysis Population): 2 separate PEx Analysis Populations have been defined: 1) Protocol-Defined PEx Population (patients who experience a PEx with $\geq 4/12$ positive Fuch symptoms and treated with an IV antibiotic); 2) Overall PEx Population (patients who experience a PEx treated with an oral or IV antibiotic). This differs from the Protocol, wherein only one PEx Population, defined by patients treated with an IV antibiotic, is defined	To distinguish between PEx defined by Investigators based on clinical judgment and PEx defined by a standard criteria.
Final v5.0 (dated: 08OCT2019)	Protocol Section 12.2 (Analysis Population)	SAP Section 3.3. (Analysis Population): Addition of a definition of the Healthy Control Population used for the first secondary parameter.	To define the Healthy Control Population to be used in the assessment of pharmacodynamic parameters (AA, DHA and AA/DHA ratio)
Final v5.0 (dated: 08OCT2019)	Protocol Section 6 (Study Objectives-Secondary Objectives); Protocol Section 7.1.3 (Secondary Endpoints)	SAP Section 3.15 (Analysis of Secondary Endpoints): assessment of Overall PEx has been added, in addition to the assessment of Protocol-Defined PEx	To distinguish between PEx defined by Investigators based on clinical judgment and PEx defined by a standard criteria.
Final v5.0 (dated: 08OCT2019)	Protocol Section 12.5.1 (Adverse Events), 12.5.2 (Clinical Laboratory Assessments)	SAP Section 3.18 (Analysis of the Safety Endpoints): removal of the methodology related to the Fisher's Exact test to assess between-group differences in treatment emergent and clinically significant AEs	This phase 2 trial was not designed to test specified hypotheses about safety. Therefore, the Fisher's exact test will not be performed. AEs will be presented descriptively, and a qualitative evaluation will be performed.

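### The written methods in SAP 3.9 omit the graded laboratory summaries and Grade 3-4 listing planned in Protocol 12.5.2, and SAP 5 does not log the omission

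*SAP*

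**What the plan says.** Protocol 12.5.2 plans laboratory reporting in three parts.

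- **Descriptive part.** Summary statistics by time point, change from baseline by arm, and a shift table against the reference range.
- **Graded part.** The first item concerns worst grade: "Summary tables of laboratory results will be prepared to examine the worst toxicity grade on study". The second, which carries a qualifier, is a set of tables "of patients by maximum post-baseline toxicity will be presented, as appropriate". The third is a listing: "Patients who develop Grade 3-4 laboratory toxicities will also be listed separately".
- **Test.** An exploratory Fisher's exact test comparing the arms on the "incidence of laboratory toxicities graded according to CTCAE grading outlined in section 11.1.1.1".

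SAP 3.9 carries over the first part. Laboratory variables are shown "at each time point using descriptive statistics (mean, standard deviation, median, minimum, and maximum"), with change from baseline by arm and patient counts for "shift changes from baseline (normal/missing, high, and low according to the reference range) to the highest/lowest laboratory evaluation during the TEAE period". It then ends. SAP 3.18, on safety endpoints, says nothing about grading laboratory values.

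SAP 5, the table of departures from the protocol, has one entry that cites Protocol 12.5.1 and 12.5.2. It records the removal of Fisher's exact test, described in terms of adverse events, and gives as the reason: "This phase 2 trial was not designed to test specified hypotheses about safety". SAP 6, the version history, does not mention laboratory data.

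Two other provisions bear on the point. Safety laboratory tests are named in the primary safety endpoint (Protocol 7.1.1, SAP 2.8.1.1). The liver-function exclusion applies only to "ALT and/or AST > 2.5 x ULN" (Protocol synopsis and 8.2, SAP 2.7.2), so a patient may enter with a transaminase already above the normal range.

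**The concern.** The graded part of Protocol 12.5.2 is what shows how many patients in each arm reached a severe laboratory value. It is absent from the SAP's written methods. A reader who checks SAP 5 for departures from 12.5.2 finds only the test removed and would assume that the rest stands.

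The logged reason does not cover the gap. That the trial was not built to test safety hypotheses is a reason to drop a test. Grade tables and a listing test nothing. The same entry says that adverse events will be presented descriptively, which sits comfortably with keeping them.

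At stake is one component of a primary endpoint. If the SAP is followed as written, the laboratory section of the report could give no patient counts by severity and arm, and no list of the patients with Grade 3-4 values. By contrast, SAP 3.8 keeps magnitude thresholds for blood pressure, heart rate and QT/QTc.

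**Working it through.** The plan gives no figure to reproduce here. The check compares the texts and then looks at what the retained outputs can show.

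**Step 1: outputs side by side.**

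| Output | Protocol 12.5.2 | SAP 3.9 / 3.18 | Logged in SAP 5 |
|---|---|---|---|
| Descriptive statistics by time point | yes | yes | not needed |
| Change from baseline by arm | yes | yes | not needed |
| Reference-range shift table | yes | yes | not needed |
| Worst-grade summary tables | yes | absent | no |
| Cross-tabulation by maximum toxicity | yes, as appropriate | absent | no |
| Grade 3-4 laboratory listing | yes | absent | no |
| Fisher's exact test, exploratory | yes | absent | yes |

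Four outputs are absent and one of them is logged. The other three are descriptive.

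**Step 2: what the shift table can register.** For a value x in multiples of ULN, the upper category is high if x > 1. The pairs below are assumed, for illustration only.

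| Baseline | Worst value | Cell |
|---|---|---|
| 0.8 | 1.1 | normal to high |
| 0.8 | 10 | normal to high |
| 2.0 | 2.2 | high to high |
| 2.0 | 15 | high to high |

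Rows 1 and 2 share a cell, and so do rows 3 and 4. The table therefore does not separate a small rise from a large one. A baseline of 2.0 x ULN is eligible for ALT or AST, since 2.0 < 2.5. For anyone entering above 1 and up to 2.5 x ULN there is no category above high, so no upward shift can be recorded. A downward shift still can.

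**Step 3: what the other retained outputs add.**

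- *Visit-level minimum and maximum.* Chemistry is drawn at six visits after baseline (Days 21, 49, 77, 105, 161 and 189). The maximum is the single most extreme value in an arm at a visit. It is the same whether one patient or several reached that level, so it gives no patient count.
- *Change from baseline.* This is summarised over the arm and is not tied to a grade or to a patient's worst value.
- *Adverse events.* Under Protocol 11.1.1 a laboratory abnormality becomes an adverse event if it leads to discontinuation, treatment or further work-up, or is associated with signs or symptoms that the investigator considers potentially important. Such events are graded by CTCAE (11.1.1.1) and reach the SAP 3.18 table of maximal severity. An abnormality that meets none of these conditions does not appear there, whatever its grade.

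No combination of these yields patient counts by worst laboratory grade and arm.

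**Step 4: number of patients.** Let p be the proportion entering with ALT or AST above ULN and within the limit. The number who cannot show an upward shift in that analyte is 136 × p, at the minimum sample size of 136. Each percentage point of p is 136 × 0.01 = 1.36 patients. The documents do not give p.

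**The case against.** The strongest objection is that most of the SAP is not in the text reviewed. Section 7, the mock tables, starts at page 43 of a 237-page document. If it runs to the end, that is 237 − 43 + 1 = 195 pages of shells, updated for version 6.0. Graded laboratory tables and a Grade 3-4 listing could well be there. This stands, and it limits the point to the written methods and the change log.

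Second, silence is not withdrawal. The SAP says that it describes analyses performed under the protocol, and nowhere does it say that the graded outputs are dropped. SAP 3.18 also does not repeat the protocol's listings of deaths and serious adverse events, which suggests that the prose does not enumerate listings. This weakens any inference of a deliberate deletion, particularly for the listing. It explains less well why the two kinds of graded summary table are missing from a section that otherwise follows its protocol counterpart closely.

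Third, severe values would not vanish. A transaminase of 10 x ULN would show as an arm's maximum at that visit, and an abnormality leading to intervention would be a graded adverse event. This also stands, and it is why the loss described here is of counts and patient identification, not of all visibility.

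Fourth, Protocol 5.4.4.1 reports that biochemical and hematological parameters were unaffected in the Phase Ib study. That study had 15 patients treated in 21-day cycles. Protocol 7.1.2 gives longer treatment and a larger sample as its reasons for making safety a primary endpoint here.

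**Conclusion.** The point holds for the SAP's written text. Three descriptive outputs planned in Protocol 12.5.2 are missing from SAP 3.9, and the SAP 5 entry citing that section covers only Fisher's test. Followed as written, the SAP gives no patient counts by worst laboratory grade and arm. Its shift table is blind to severity among patients who become high, and to any rise among patients already high at entry. The size cannot be put in patients, because the baseline distribution is not given. The multiples of ULN used above are assumptions.

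A reader might infer more than the documents support:

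- *That the sponsor has removed graded laboratory analysis from the trial.* The mock tables may contain it.
- *That severe worsening would be invisible.* That limit belongs to the shift table. Visit maxima and graded adverse events remain.
- *That all safety testing is gone.* The between-arm Fisher tests were exploratory and their removal is logged with a reason. SAP 3.18 still plans a Spearman correlation for retinol and retinol-binding protein.
- *That pooling missing with normal at baseline is a SAP deviation.* Protocol 12.5.2 pools them too.

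This is a correction worth making before the tables are run. It does not touch the efficacy conclusion.

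**What to change.** In SAP 3.9, restore by arm the worst-grade summaries, the cross-tabulation by maximum post-baseline toxicity, and the Grade 3-4 laboratory listing, using the CTCAE grading that the protocol cites. The cross-tabulation is best laid out as baseline grade by worst post-baseline grade, so that patients abnormal at entry can be followed. The protocol does not prescribe that layout, so it is a recommendation.

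If the mock tables already contain these outputs, align the SAP 3.9 text with them and cite them. If any output is meant to be left out, SAP 5 should say so and give a reason that applies to descriptive tables.

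Two small additions can go in at the same time. SAP 3.18 points to Section 3.8 for laboratory assessments, but they are in 3.9. Showing missing baseline separately from normal would be an optional improvement.

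The cost is a little programming of standard tables from central-laboratory data that the trial already collects. There is no change to trial conduct and no new data collection.

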3.10 Ophthalmologic Examinations and Night Vision Questionnaire

The answers to the NVQ questionnaires and the resulting levels will be summarized by treatment group. The results (normal/abnormal, new adverse findings) of the planned during- and post-study ophthalmologic examinations will be presented, alongside the baseline examination and summarized by treatment group. Ad-hoc examinations and findings will also be presented alongside the baseline examination. All reported symptoms of nyctalopia and hemeralopia will be tabulated by treatment group. Reported symptoms confirmed by objective measures will be tabulated separately by treatment group. Individual data will be presented in listings.

No statistical analyses of ophthalmologic data are planned

3.11 Plasma Retinol and Retinol Binding Protein

Plasma retinol and retinol binding protein values will be presented at each time point using descriptive statistics (mean, standard deviation, median, minimum, and maximum). The number and percentage of subjects reporting low, normal and high values at each visit will also be described by treatment group.

3.12 Adherence to Treatment (Compliance)

Study drug compliance will be performed on the Safety population. Study drug compliance will be assessed by calculating as follows: $100 \times (1 - [\text{total number of days of study drug interruption}] / [(\text{duration of study drug exposure}) - (\text{total duration of planned drug free intervals})])$. The total number of days of study drug interruption is defined as the sum of (number of days of each study drug interruption), where number of days of each study drug interruption is defined as the interruption end date minus the corresponding interruption start date plus 1 day. Treatment compliance percentages will be summarized descriptively as continuous variables (number, mean, SD, median, minimum, and maximum). The percentage of patients whose compliance is $< 80\%$ or $\geq 80\%$ will be summarized, by treatment group.

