9.4 Study Drug Treatment

The total duration of study treatment is 6 cycles of 21 consecutive days of either LAU-7b or placebo treatment each followed by a 7-days treatment-free period. This represents approximately 24 weeks in total.

During the study, eligible CF patients aged 18 years and older will be randomized, after stratification according to 1- FEV₁ severity categories, 2- Number of PEx episodes in prior year, and 3- Co-administration or not of Kalydeco®, Orkambi®, Symdeko® or another commercially available CFTR modulator product, using a 1:1 allocation to LAU-7b 300 mg per day or matching placebo, in a double blind fashion. Treatment assignments will be determined through the IWRS system.

In all cases, the study treatment will be administered on top of current Standard of Care therapies.

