9.4.4 Storage, Dispensing and Compliance Verification of Study Drug

Upon receipt of the study drug shipper container, the investigator should record the receipt, date, time, and temperature of the product based on inspection or on the temperature logger reading. Any study drug that arrives in improper storage conditions or is damaged in any way must be reported to the Laurent designee,

as instructed in the Pharmacy Manual, as soon as possible and shall not be administered until instructed otherwise.

At the clinical sites, the study drug kits will be stored in a suitable -20°C (-15°C to -25°C) freezer in a secure location with limited access. Most preferably, the storage freezer will be continually monitored and alarmed in order to document any excursion outside the desired temperature range. Alternatively, the use of a calibrated min-max thermometer in the storage freezer is acceptable as long as the thermometer readings are taken daily during weekdays, at a minimum.

Upon instructions from the IWRS, the pharmacy/site staff will, at the time of dispensing, formally identify and remove the assigned Patient Kit box(es) from the -20°C freezer and will check the expiry date on the labels on the Patient Kit box(es), at a minimum. Where applicable, the necessary Patient Kits will be sent (in an isolated container with ice packs) to the site staff actually dispensing the study drug to the patients.

The study drug may only be used as directed in this APPLAUD protocol. It is against regulations to use investigational products for other purposes.

Prior to some of the end-of-cycle visits (Days 21, 77 and 161), the patients will be reminded to bring their used box(es) of supplies including the capsule containers, for drug accountability. The number of capsules consumed per cycle will be recorded for the 21 days of study drug treatment. Patients will be encouraged toward full compliance with instructions.

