12.3.3 Study Drug Compliance

Study drug compliance will be performed on the Safety population. Study drug compliance will be assessed by calculating as follows: $100 \times (1 - [\text{total number of days of study drug interruption}] / [(\text{duration of study drug exposure}) - (\text{total duration of planned drug free intervals})])$. The total number of days of study drug interruption is defined as the sum of (number of days of each study drug interruption), where number of days of each study drug interruption is defined as the interruption end date minus the corresponding interruption start date plus 1 day. Treatment compliance percentages will be summarized descriptively as continuous variables (number, mean, SD, median, minimum, and maximum). The percentage of patients whose compliance is $<80\%$ or $\geq 80\%$ will be summarized, by study group.

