3.3 Analysis Population

The Intent-to-treat (ITT) Population will include all patients randomized to a treatment group who complete the baseline evaluations, regardless of having received any study treatment or not. The ITT population will be used for the primary analyses of all study endpoints, taking into consideration the specific populations described below. The patients will be kept in their randomized treatment arm for the analyses.

The Per Protocol (PP) Population will include all patients randomized to a treatment group to whom at least 5 cycles of study treatment are administered in accordance with the protocol, defined as at least 80% compliance. The PP population will serve as the basis for secondary analyses of

all study endpoints, taking into consideration the specific populations described below. The patients will be kept in the treatment arm that they actually received for the analyses.

The FEV₁ Population is a subset of the PP population and will include all patients who have validated FEV₁ values (values judged to be obtained from adequate expiratory curves by central review) for at least 4 time points of the study comprising at the minimum the baseline and Day 161 assessments. This population will be used for the secondary analyses of all FEV₁-related endpoints. The patients will be kept in the treatment arm that they actually received for the analyses.

The Protocol-Defined PEx Subset Population will include all patients who experience a protocol - defined PEx episode (\geq 4/12 Fuch symptoms and use of IV antibiotic) during the study after completing at least one cycle of study drug treatment. The patients will be kept in the treatment arm that they actually received for the analyses.

The Overall PEx Subset Population will include all patients who experience an oral or IV antibiotic treated PEx episode during the study after completing at least one cycle of study drug treatment. The patients will be kept in the treatment arm that they actually received for the analyses.

The Safety Population will include all patients randomized to a treatment group who received at least one dose of study drug treatment. This population will serve as the basis for analyses of all safety endpoints. The patients will be kept in the treatment arm that they actually received for the analyses.

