3.5 Treatment Exposure and Dosing

The duration of study drug exposure is defined as follows: last dose date minus first dose date plus 1 day, regardless of any interruptions in dosing. If the last dose date of study drug is missing, the patient's discontinuation or completion date will be used for analysis purpose. Duration of study drug exposure will be summarized descriptively as a continuous variable (number, mean, SD, median, minimum, and maximum), by treatment group, using the Safety population.

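### The compliance formula uses interruption dates and ignores the recorded capsule counts, so it can misclassify patients around the 80% cut that defines the per-protocol population

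*SAP*

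**What the plan says.** - **The formula.** SAP 3.12 sets compliance to 100 × (1 − I / (E − P)), where I is total days of interruption, E is duration of exposure and P is the planned drug-free time. For I, the "number of days of each study drug interruption is defined as the interruption end date minus the corresponding interruption start date", plus one day. Protocol 12.3.3 gives the same formula. Neither has a capsule term.
- **Exposure.** SAP 3.5 defines E as "last dose date minus first dose date plus 1 day, regardless of any interruptions in dosing".
- **What is collected.** Protocol 9.4.4, on compliance verification, states: "The number of capsules consumed per cycle will be recorded for the 21 days of study drug treatment".
- **Where the result is used.** Under SAP 3.3, PP requires that "at least 5 cycles of study treatment are administered in accordance with the protocol, defined as at least 80% compliance". Protocol 12.2 has the five-cycle condition without a percentage. SAP 3.3 does not refer to 3.12 and gives no other formula. It makes the FEV1 population a subset of PP.
- **Schedule.** Protocol 9.4 sets "6 cycles of 21 consecutive days of either LAU-7b or placebo treatment each followed by a 7-days treatment-free period". The synopsis gives three capsules per dosing day. Protocol 9.5 says that a patient who misses the start of a cycle should begin it as soon as possible, with later visits moved accordingly.
- **Meaning of an interruption.** The only definition is the action-taken category in Protocol 11.1.1.3, which ties it to an adverse event.

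**The concern.** The trial records a direct measure of intake and then decides PP membership from an indirect one. The indirect measure has two weaknesses that act in opposite directions.

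First, it works in whole days of logged interruption. A day on which some capsules are taken is not an interruption, so partial dosing cannot register. A forgotten day registers only if someone logs it, and neither document says that it must be logged.

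Second, the numerator and denominator are on different bases. The denominator removes planned drug-free days. The numerator counts every calendar day from the start to the end of an interruption, including any planned drug-free days inside it.

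At stake is who enters PP. That population carries a confirmatory analysis of the primary endpoint (SAP 3.14), secondary analyses of all endpoints (SAP 3.3) and the exploratory analyses (SAP 3.16). The table of patients below and at or above 80% is affected too.

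**Working it through.** **Full course.** Exposure is 6 × 28 − 7 = 161 days, which matches the End-of-Cycle 6 visit on Day 161 in the schedule of events. Five drug-free weeks fall inside it, so P = 5 × 7 = 35. The denominator is 161 − 35 = 126, equal to 6 × 21 dosing days or 3 × 126 = 378 capsules. By count, 25 wholly missed days leave 101/126 = 80.2% and 26 leave 100/126 = 79.4%.

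**Formula too high.**
- Two of three capsules every day: I = 0, so the formula gives 100%. The count is 252/378 = 66.7%.
- Five scattered missed days per cycle, none logged: the formula gives 100%. The count is (126 − 30)/126 = 96/126 = 76.2%.

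**Formula too low, fixed schedule.** Take one interruption logged as Days 15-42.
- Calendar days: 42 − 15 + 1 = 28. Days 22-28 are planned off days, so missed dosing days are 28 − 7 = 21.
- Formula: 1 − 28/126 = 77.8%. Doses taken: 105/126 = 83.3%.
- On this schedule, any single interruption of 26 to 32 calendar days between Day 2 and Day 160 fails by formula (79.4% down to 74.6%) and passes by count (80.2% to 84.9%), if 80% applies overall.

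**Formula too low, with the Protocol 9.5 shift.** Cycle 2 starts on the first day after the interruption and all later cycles move with it.

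| Interruption | Cycle 2 starts | Last dose | E − P | Formula | Doses taken |
|---|---|---|---|---|---|
| Days 15-42 | Day 43 | Day 175 | 175 − 35 = 140 | 1 − 28/140 = 80.0% | 119/126 = 94.4% |
| Days 15-43 | Day 44 | Day 176 | 176 − 35 = 141 | 1 − 29/141 = 79.4% | 119/126 = 94.4% |

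In both rows the patient misses only Days 15-21 of Cycle 1 (126 − 7 = 119 dosing days taken) and completes Cycles 2 to 6. One extra calendar day before restart moves the patient from pass to fail with no change in doses taken.

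**Removing off days from the numerator.** For Days 15-43, dropping Days 22-28 leaves 29 − 7 = 22 days and 1 − 22/141 = 84.4%. The patient passes, but the figure is still below 94.4%, because the 15 days of delay (Days 29-43) count as missed although the cycle was later taken in full. On the fixed schedule the same correction gives 1 − 21/126 = 83.3%, which agrees with the count.

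**The case against.** The strongest reply has five parts.

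1. *The fixed-schedule example is not decisive.* Under Protocol 9.5 the Days 15-42 patient scores exactly 80.0% and passes. If SAP 3.3 means 80% in each of at least five cycles, then on a fixed schedule that patient has 14/21 = 66.7% in Cycle 1 and 7/21 = 33.3% in Cycle 2, and is out of PP by capsule count as well. This stands. The Days 15-43 case with the shift does not have this weakness by count: it has five complete cycles and passes on either reading. Its failure by formula does assume that 80% applies to the overall figure, which is the only one SAP 3.12 defines.
2. *Off days need not be logged as interruption.* Entering Days 15-21 and Days 29-42 separately gives 21 days and 83.3%. True, but nothing in either document requires the split, so the same patient can be in or out of PP depending on date entry.
3. *Persistent partial dosing is unlikely.* Packs hold 21 sachets for a 21-day cycle, which suggests one sachet per daily dose, and Protocol 11.1.1.3 has no individual dose-reduction category. The two-of-three case therefore shows what the formula cannot detect, not a pattern to expect.
4. *Forgotten days may be logged.* A reader might infer that scattered missed doses will go uncounted. The documents do not support that: it depends on e-CRF instructions that they do not contain. If each wholly missed day is entered as a one-day interruption, those days are captured; partial doses still are not.
5. *Long gaps may be few.* Protocol 8.4.1 lists prolonged interruption among the grounds in its stopping guide. This bears on frequency, not on whether the rule is sound.

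**Conclusion.** The rule is faulty as written, and the data needed to correct it are already recorded. It can misclassify patients around the 80% cut in both directions: 100% against 66.7% or 76.2% when dosing is partial or missed days go unlogged, and 79.4% against 94.4% when an interruption is logged across an off period and the cycles shift.

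These figures rest on three assumptions: the SAP 3.12 formula is the compliance measure meant in SAP 3.3, 80% is applied overall, and the interruption is entered as one continuous span. The partial-dose figure needs only the first.

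Two stronger conclusions are tempting and are not supported. One is that a known share of PP is misclassified: the documents give neither the frequency of such patterns nor the logging rules, so no number can be derived. The other is that the trial's main result is at risk. SAP 3.14 judges success in the intent-to-treat population, which does not depend on compliance. The effect stops at PP, the nested FEV1 population and the compliance table. The change should be made, but the primary analysis does not turn on it.

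**What to change.** - In SAP 3.12, define compliance as capsules taken divided by capsules scheduled, from the counts recorded under Protocol 9.4.4, over cycles due before discontinuation.
- Take the scheduled number from the regimen in force and do not fix it at three a day. Protocol 7.2.4 allows an arm-wide reduction from 300 to 200 mg/day. If that were done with fewer capsules, a fixed denominator would score fully adherent patients as low as 2/3 = 66.7%.
- State a rule for packs that are not returned.
- If interruption dates are kept, for example as a fallback, exclude planned drug-free days from the numerator.
- In SAP 3.3, cite this definition and state whether 80% applies per cycle or overall.
- Record the departure from Protocol 12.3.3 in SAP Section 5.

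The cost is minor wording and programming, with no new data collection. The drawback is reliance on patients bringing back their packs.
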